9.4.1.2. Mini Mental State Examination

The MMSE is a brief, validated 30-point questionnaire that is used to screen for cognitive impairment.²¹ The MMSE rates subjects on orientation (total score, 10), registration (total score, 3), attention, calculation (total score, 5), recall (total score, 3), and language (total score, 9). The maximum score is 30. The lower the score the more pronounced the impairment.

9.4.1.3. California Verbal Learning Test – Second Edition

The CVLT-II is a face-to-face comprehensive neuropsychological measure of verbal memory in individuals 16 to 89 years old. It is designed to quantify components of verbal learning, retention and retrieval.¹³ The CVLT-II differs from the original CVLT in that new word stimuli are used, new and larger normative database was collected, addition of a forced choice recognition procedure at the end, as well as computerized scoring. Sixteen (16) words are read out to the participants five times with the instruction to memorize as many words as possible each time. Each of the words belongs to one of four categories: thus, there are four fruits, four herbs and spices, etc. The participants are asked to recite the words they could recollect immediately following each presentation (immediate recall or IR) and after an interval of at least 20 minutes (delayed recall or DR), which is then followed by a 32 item recognition subtest.

9.4.2. Clinical Scales and Functional Measures

9.4.2.1. Clinical Dementia Rating Scale – Sum of Boxes

The CDR is a global clinical scale with established diagnostic and severity-ranking utility widely used in clinical trials yielding global and Sum of Boxes (SB) scores (CDR-SB). The CDR global

score is used in AD trials as a global measure of disease progression. The CDR is rated based on subject and informant reports. It does not directly rely on psychometric tests thereby avoiding learning effects. The CDR has also been adapted for routine clinical use in tertiary clinics and chronic care facilities. The CDR assesses three domains of cognition (memory, orientation, judgment/problem solving) and three domains of function (community affairs, home/hobbies, personal care) using semi-structured interviews of both the study subject and a companion/informant carried out by a trained rater and scored using a standard methodology. Each domain is rated on a 5-point scale of functioning as follows: (0) no impairment; (0.5) questionable impairment; (1) mild impairment; (2) moderate impairment; and (3) severe impairment (personal care is scored on a 4-point scale without a 0.5 rating available). An algorithm is used for integrating the information obtained into an overall score, i.e., “CDR Global” score ranging from 0 to 3 with 0 having no dementia and 3 having severe dementia.

The scores for the six domains (ranging from 0 to 3) tested can be summed to obtain the CDR Sum of Boxes or CDR-SB score, with scores ranging from 0 to 18.

The CDR-SB scores can be used to stage patients.⁴⁷

The CDR comprehensively assesses both cognitive and functional disability in AD patients and is expected to be particularly useful for studies in early stages of AD.⁷

During the study the CDR will be audiotaped (including informant information) and reviewed centrally. The subject’s and informant’s approval or disapproval for such recording will be documented in the source documents.

9.4.2.2. Cognitive Function Index (CFI)

The CFI is a modified version of the Mail-in Cognitive Function Screening Instrument⁶⁰, a subject- and study partner-reported outcome measure developed by the Alzheimer’s Disease Cooperative Study (ADCS). This assessment includes 15 questions that assess the subject’s perceived ability to perform high level functional tasks in daily-life and their sense of overall cognitive functional ability. Study subjects and their study partners independently rate the subject’s abilities.

9.5. Pharmacokinetics

9.5.1. Evaluations

Venous blood samples for analysis of JNJ-54861911 in plasma will be collected at the time-points indicated in the Time and Events Schedule.

Blood samples will be used to evaluate the plasma pharmacokinetics of JNJ-54861911. Samples collected for analyses of JNJ-54861911 plasma concentration may additionally be used to evaluate safety or efficacy aspects that address concerns arising during or after the study period or for the evaluation of relevant biomarkers.

The CSF samples (12 mL each) collected for biomarker research as outlined in Section 9.3.1.1 CSF Biomarkers, will be used, in addition to analysis of relevant biomarkers concentrations, for the analysis of JNJ-54861911 concentrations.

9.5.2. Analytical Procedures

Pharmacokinetics

Plasma will be analyzed to determine concentrations of JNJ-54861911 using a validated, specific, and sensitive LC-MS/MS method by or under the supervision of the sponsor. JNJ-54861911 concentrations will be analyzed in CSF (only post-dose samples) with a qualified LC-MS/MS assay.

If required, some plasma and CSF samples may be analyzed to document the presence of circulating metabolites using a qualified research method.

9.5.3. Pharmacokinetic Parameters

Population PK analysis of plasma and CSF concentration-time data of JNJ-54861911 will be performed using nonlinear mixed-effects modeling. Data may be combined with those of a selection of Phase 1 studies to support a relevant structural model. Based on the individual plasma and CSF concentration-time data, if sufficient data are available, the following PK parameters of JNJ-54861911 may be estimated at steady state in subjects receiving a dose of JNJ-54861911 using population PK modeling:

C_{\max} maximum plasma/CSF concentration

AUC_{τ} area under the plasma/CSF concentration-time curve from 0 to τ hours post dosing (time τ is the dosing interval)

CSF-related parameters will only be estimated if allowed by the model, due to the limited number of samples collected for each subject. Additional analyses may be conducted according to a population PK analysis plan and results will be presented in a separate report.

The parameters of interest for the statistical analysis will be the log-transformed estimated dose normalized AUC and C_{\max} . All ratios will be calculated as differences of least square means of the appropriate model on the log-scale, and will be presented after back-transformation to the original scale with the corresponding 90% confidence intervals (CIs).

Based on the individual plasma concentration-time data, using the actual dose taken and the actual sampling times, PK parameters and exposure information of JNJ-54861911 will be derived using population PK modelling. Baseline covariates (e.g., body weight, age, sex, CrCL, race) may be included in the model, if relevant.

9.6. Sample Collection and Handling

PK and PD (biomarker) sampling/assessment times and sampling volumes can be adapted without protocol amendment provided that the maximal volume collected per subject specified per protocol will not be exceeded.

Refer to the Time and Events Schedule for the timing and frequency of all sample collections.

The exact dates and times of blood and CSF sampling must be recorded in the CRF or lab requisition form.

Baseline and on-treatment CSF samples should be taken at approximately the same time of day (with an allowable window of 3 hours), with the on-treatment samples sample being collected postdose.

For CSF sampling, local site SOPs may be applied for performing the actual lumbar puncture (not the collection), provided they are at least as restrictive as the criteria defined per protocol.

Instructions for the collection, handling, storage, and shipment of samples will be provided in a separate lab manual. Collection, handling, storage, and shipment of samples must be under the specified, and where applicable, controlled temperature conditions as indicated in the lab manual.

All the assays and instruments used in this study will be performed by trained operators at the Sponsor or designated laboratories in Europe or the US on coded samples.

Venous blood samples and CSF samples may be stored and used for future analysis of JNJ-54861911 metabolites and exploratory proteomics and metabolomics or other markers related to AD or neuropsychiatric disorders. Additionally markers of blood brain barrier integrity or subtle procedure related inflammatory changes may be examined.

Samples may be provided to external partners for exploratory (CSF) biomarker research related to AD upon completion of the study.

10. SUBJECT COMPLETION/WITHDRAWAL

10.1. Completion

Subjects are considered to have completed the study if they discontinued treatment with JNJ-54861911 (provided by the sponsor) for any reason (i.e., disease progression, unacceptable toxicity, sponsor terminates the study, or alternative access to JNJ-54861911 becomes available and feasible (i.e., commercial source of JNJ-54861911) and had a follow-up safety assessment approximately 30 days after the last dose of JNJ-54861911. Subjects who die while receiving treatment also are considered to have completed the study.

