10.2. Discontinuation of Study Treatment

If a subject's study treatment must be discontinued before the end of the treatment regimen, this will not result in automatic withdrawal of the subject from the study.

The following specific individual rules for stopping study treatment will apply:

- Mean QTcF interval of > 500 msec if confirmed upon repeat ECG, and/or mean QTcF increase versus baseline of > 60 msec if confirmed upon repeat ECG (all triplicate recordings).
- The investigator believes that for safety reasons (e.g., adverse event) it is in the best interest of the subject.
- Liver enzyme elevation between Weeks 52 and 64, including any of the following:
 - ALT or AST $>5\times$ ULN
 - ALT or AST $>3\times$ ULN and total bilirubin $>2\times$ ULN or INR >1.5
 - ALT or AST $>3\times$ ULN with the appearance of fatigue, nausea, vomiting, right upper quadrant pain or tenderness, fever, rash, and/or eosinophilia $>5\%$
- Liver enzyme elevation after Week 64, including any of the following:
 - ALT or AST $>8\times$ ULN
 - ALT or AST $>5\times$ ULN for more than 2 weeks
 - ALT or AST $>3\times$ ULN and total bilirubin $>2\times$ ULN or INR >1.5
 - ALT or AST $>3\times$ ULN with the appearance of fatigue, nausea, vomiting, right upper quadrant pain or tenderness, fever, rash, and/or eosinophilia $>5\%$

Re-initiation of study treatment should only be done after consultation with the sponsor medical monitor and in mutual agreement between the sponsor and the study center. If a subject permanently discontinues study treatment before the end of the treatment phase, the subject will be asked to complete the Week 52 assessments, including CSF sampling, if not yet obtained earlier. At a minimum, the subject will be asked to complete the End-of-Treatment Visit (Follow-up visit) as per the Time and Events Schedule.

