10.3. Withdrawal From the Study

A subject will be withdrawn from the study for any of the following reasons:

- Lost to follow-up
- Withdrawal of consent or assent
- Death
- Noncompliance

If a subject is lost to follow-up, every reasonable effort must be made by the study site personnel to contact the subject and determine the reason for discontinuation/withdrawal. The measures taken to follow-up must be documented.

When a subject withdraws before completing the study, the reason for withdrawal is to be documented in the CRF and in the source document. Study drug assigned to the withdrawn subject may not be assigned to another subject.

Subjects who are withdrawn will not be replaced.

Any subject who withdraws after receiving the study drug will be asked, if not yet obtained, to have the Week 52 assessment performed. At least the subjects should have a follow-up evaluation as described in Section 9.1.5

Withdrawal From the Use of Samples in Future Research

The subject may withdraw consent for use of samples for research (refer to Section 16.2.5, Long-Term Retention of Samples for Additional Future Research). In such a case, samples will be destroyed after they are no longer needed for the clinical study. Details of the sample retention for research are presented in the main ICF.

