11.5. Safety Analyses

All subjects receiving at least one dose of study drug will be included in the safety analysis. Descriptive statistics will be computed.

Adverse Events

The verbatim terms used in the CRF by investigators to identify adverse events will be coded using the Medical Dictionary for Regulatory Activities (MedDRA). All reported adverse events with onset during the treatment phase (i.e., treatment-emergent adverse events, and adverse events that have worsened since baseline) will be included in the analysis. For each adverse event, the percentage of subjects who experience at least one occurrence of the given event will be summarized by treatment group. Adverse events will also be tabulated by severity and by relationship to study drug and will be presented by treatment group. Serious adverse events will be summarized separately.

Summaries will be provided for all subjects receiving at least one dose of study drug in this study, and will include adverse events from this study as well as any preceding studies (e.g., study JNJ-54861911ALZ1005, JNJ-54861911ALZ2002 or any future Phase 1b or Phase 2 JNJ-54861911 clinical studies) as applicable for subjects who previously participated in that study, where appropriate.

Summaries, listings, datasets, or subject narratives may be provided, as appropriate, for those subjects who die, who withdraw due to an adverse event, or who experience a severe or a serious adverse event. Subjects with AESIs may be counted or listed.

Clinical Laboratory Tests

Laboratory data will be summarized by type of laboratory test. Descriptive statistics will be calculated for each laboratory analyte at baseline and at each scheduled time point, and for changes from baseline.

The number and percentage of subjects experiencing a laboratory result below or above normal reference ranges will be provided for each laboratory analyte by treatment group.

A listing of subjects with any laboratory result outside the reference ranges will be provided.

Electrocardiogram (ECG)

Heart rate and ECG intervals (RR, PR, QRS, and QT) as well as corrected QT intervals according to Bazett's formula (QTcB) and Fridericia's formula (QTcF) from the 12-lead ECG will be summarized at baseline and at each scheduled time point and for changes from baseline using descriptive statistics.

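### Does it matter that an on-treatment death is both a completion and a withdrawal, and that the safety section speaks of withdrawing for an adverse event?

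*Protocol*

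**What the plan says.** Section 10.1 gives two routes to completion. The first reads "Subjects are considered to have completed the study if they discontinued treatment with JNJ-54861911 (provided by the sponsor) for any reason", with unacceptable toxicity among the examples, provided a safety follow-up took place about 30 days after the last dose. The second reads "Subjects who die while receiving treatment also are considered to have completed the study".

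Section 10.2 covers stopping treatment early and says that "this will not result in automatic withdrawal of the subject from the study". One of its stopping rules is "The investigator believes that for safety reasons (e.g., adverse event) it is in the best interest of the subject".

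Section 10.3 begins "A subject will be withdrawn from the study for any of the following reasons" and gives four: loss to follow-up, withdrawal of consent or assent, death, and noncompliance. It adds: "When a subject withdraws before completing the study, the reason for withdrawal is to be documented in the CRF and in the source document".

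Section 11.5, under adverse events, says: "Summaries, listings, datasets, or subject narratives may be provided, as appropriate, for those subjects who die", and continues with those "who withdraw due to an adverse event, or who experience a severe or a serious adverse event".

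**The concern.** There are two apparent faults.

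- **Death.** A subject who dies while taking study drug has completed under 10.1 and is withdrawn under 10.3. If sites or programmers follow different sections, the same event is coded in two ways.
- **Adverse-event stops.** Section 10.2 makes such a stop a discontinuation of treatment, 10.3 has no adverse-event reason, and 10.1 can count the subject as a completer. Read literally, the group that 11.5 names for withdrawing because of an adverse event would be nearly empty. A subject who stopped drug for an event that was neither severe nor serious, and stayed in the study, would be missed.

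Long-term safety and tolerability is the primary objective. Stops due to adverse events are a standard measure of tolerability, so losing them, or misclassifying deaths, would matter in this trial.

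**Working it through.** The protocol gives no figure to reproduce. Section 11.2 says that the study is not powered, and section 2.2 plans no hypothesis test. The check is a comparison of the sections.

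**1. Death on treatment**

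| Section | Status |
|---|---|
| 10.1 | Completed |
| 10.3 | Withdrawn (death, no limit to deaths off treatment) |

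That is two statuses for one event. Could 10.3 be meant only for deaths after drug has stopped? The text does not say so. Section 3.4.1 also makes meeting a 10.3 criterion a reason to stop study treatment, which presupposes a subject who is still on it. The conflict therefore stands as written.

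**2. What depends on that status**

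Let N be the number of subjects dosed and d the number of on-treatment deaths, which the protocol cannot give. If 10.1 is followed, let C subjects be completers. If 10.3 is followed, there are C − d completers and d more withdrawals. The completed and withdrawn rows each move by d.

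Sections 11.1 and 11.5 base their descriptions on all subjects with at least one dose. The denominator is N under either coding, and no completer analysis is stated. The deaths stay visible in two ways: 11.5 names subjects who die as a group of their own, and 12.3.2 makes the cause of any death a serious adverse event.

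**3. Stops due to adverse events**

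The 11.5 sentence names four groups: deaths, withdrawals due to an adverse event, severe events and serious events. Take a subject who stops drug for a non-severe, non-serious event and remains in the study.

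- With withdrawal read strictly as leaving the study, the subject fits 0 of 4.
- With withdrawal read to include stopping drug, the subject fits 1 of 4.

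The strict reading finds support in places that keep the two events apart: the note after the Week 52 visit in 9.1.3, and 17.4, which mentions a reason for either event.

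Other places blur them:

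- The last column of the Time and Events Schedule is headed in part as early withdrawal, yet its footnote n describes a subject who stops study treatment.
- Section 10.3 asks sites to establish the reason for discontinuation and withdrawal as a single item.
- Section 9.1.4 lists the events that end open-label treatment and then refers to them as stopping participation.

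The wider reading of 11.5 is therefore the natural one. Section 10.2 also excludes only automatic withdrawal, so a subject may still withdraw consent because of an adverse event.

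**4. What is lost even under the strict reading**

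- Section 11.5 tabulates events that arise or worsen on treatment by group, severity and relationship to drug, whether or not drug was stopped.
- Liver and QTc stops are serious by rule under 3.4.1, so they fall in the serious group.
- Adverse events of special interest may be counted or listed.
- The reason for stopping drug must be in the source documents under 17.4, so a table of adverse-event stops can be produced without new data.

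Stated estimates changed: 0.

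**The case for a change.** The best case for acting is that this is not a detail left to the SAP. Two protocol sections instruct sites in opposite ways, and a convention chosen later by the analysts leaves both instructions in force. Stopping drug because of an adverse event is close to the heart of a tolerability study, and the only category of such stops that 11.5 names does not match section 10. The repair would be a few words.

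The first part stands: the text does contradict itself on death. It also has to be said that confining 10.3 to deaths off treatment is an inference that the wording does not support.

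The second part stands only as untidy terminology. The protocol itself uses the two terms interchangeably in several places. The 11.5 sentence says only what may be provided and excludes nothing. Which tables of adverse-event stops are produced is ordinary SAP content, and the SAP is not at hand. That a repair is cheap does not show that it gains anything.

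**Conclusion.** No change to the plan follows. On-treatment death has two dispositions where one is intended. This is a clerical inconsistency between 10.1 and 10.3, which the sponsor could tidy at any routine amendment. The 11.5 phrase is loose but not contradictory, and analysts would sensibly read it to include stopping study drug.

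The effect is confined to the completed and withdrawn rows of a disposition table, each moving by the number of on-treatment deaths. Safety denominators, adverse-event tables and the reporting of deaths and serious events stay the same, and no stated estimate changes.

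This rests on three assumptions: the SAP, which is not shown, adds no analysis restricted to completers; on-treatment deaths are coded by one rule in the database; and the reason for stopping drug is captured as 17.4 requires. If a completer analysis were added, the status of on-treatment deaths would have to be settled first.

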10.2. Discontinuation of Study Treatment

If a subject's study treatment must be discontinued before the end of the treatment regimen, this will not result in automatic withdrawal of the subject from the study.

The following specific individual rules for stopping study treatment will apply:

- Mean QTcF interval of > 500 msec if confirmed upon repeat ECG, and/or mean QTcF increase versus baseline of > 60 msec if confirmed upon repeat ECG (all triplicate recordings).
- The investigator believes that for safety reasons (e.g., adverse event) it is in the best interest of the subject.
- Liver enzyme elevation between Weeks 52 and 64, including any of the following:
 - ALT or AST $>5\times$ ULN
 - ALT or AST $>3\times$ ULN and total bilirubin $>2\times$ ULN or INR >1.5
 - ALT or AST $>3\times$ ULN with the appearance of fatigue, nausea, vomiting, right upper quadrant pain or tenderness, fever, rash, and/or eosinophilia $>5\%$
- Liver enzyme elevation after Week 64, including any of the following:
 - ALT or AST $>8\times$ ULN
 - ALT or AST $>5\times$ ULN for more than 2 weeks
 - ALT or AST $>3\times$ ULN and total bilirubin $>2\times$ ULN or INR >1.5
 - ALT or AST $>3\times$ ULN with the appearance of fatigue, nausea, vomiting, right upper quadrant pain or tenderness, fever, rash, and/or eosinophilia $>5\%$

Re-initiation of study treatment should only be done after consultation with the sponsor medical monitor and in mutual agreement between the sponsor and the study center. If a subject permanently discontinues study treatment before the end of the treatment phase, the subject will be asked to complete the Week 52 assessments, including CSF sampling, if not yet obtained earlier. At a minimum, the subject will be asked to complete the End-of-Treatment Visit (Follow-up visit) as per the Time and Events Schedule.

10.3. Withdrawal From the Study

A subject will be withdrawn from the study for any of the following reasons:

- Lost to follow-up
- Withdrawal of consent or assent
- Death
- Noncompliance

If a subject is lost to follow-up, every reasonable effort must be made by the study site personnel to contact the subject and determine the reason for discontinuation/withdrawal. The measures taken to follow-up must be documented.

When a subject withdraws before completing the study, the reason for withdrawal is to be documented in the CRF and in the source document. Study drug assigned to the withdrawn subject may not be assigned to another subject.

Subjects who are withdrawn will not be replaced.

Any subject who withdraws after receiving the study drug will be asked, if not yet obtained, to have the Week 52 assessment performed. At least the subjects should have a follow-up evaluation as described in Section 9.1.5

Withdrawal From the Use of Samples in Future Research

The subject may withdraw consent for use of samples for research (refer to Section 16.2.5, Long-Term Retention of Samples for Additional Future Research). In such a case, samples will be destroyed after they are no longer needed for the clinical study. Details of the sample retention for research are presented in the main ICF.

